Note: Participants may need to switch dosing frequency according to change in body weight (See Section 6.6 Dose Modification)

Procedure	Part B - Optional Treatment Extension - Days 86-365 (Weeks 13-52) [All participants]								
	Treatment Period							Follow-Up Period	
Study Day	Day 113 ±7 days	Day 141 ±7 days	Day 169 ±7 days	Day 211 ±7 days	Day 253 ±7 days	Day 309 ±7 days	Day 365 ±7 days	8-Week Follow-up ±7 days ¹	16-Week Follow-up ±7 days ^{1,2}
Study Week	Wk 16	Wk 20	Wk 24	Wk 30	Wk 36	Wk 44	Wk 52/EW ¹	Wk 60	Wk 68 ²
SELENA SLEDAI							X		
Vital Signs	X	X	X	X	X	X	X	X	
Weight +Height	X	X	X	X	X	X	X	X	
Symptom Driven Physical Exam ³	X	X	X	X	X	X	X	X	
Adverse Events ⁴	X	X	X	X	X	X	X	X	X
Concomitant Medications	X	X	X	X	X	X	X	X	X
Collection of device events/malfunctions	X	X	X	X	X	X	X		
Laboratory Assessments									
Hematology	X	X	X	X	X	X	X	X	

Procedure	Part B - Optional Treatment Extension - Days 86-365 (Weeks 13-52) [All participants]								
	Treatment Period							Follow-Up Period	
Study Day	Day 113 ±7 days	Day 141 ±7 days	Day 169 ±7 days	Day 211 ±7 days	Day 253 ±7 days	Day 309 ±7 days	Day 365 ±7 days	8-Week Follow-up ±7 days ¹	16-Week Follow-up ±7 days ^{1,2}
Study Week	Wk 16	Wk 20	Wk 24	Wk 30	Wk 36	Wk 44	Wk 52/EW ¹	Wk 60	Wk 68 ²
Urinalysis	X	X	X	X	X	X	X	X	
Chemistry	X	X	X	X	X	X	X	X	
Spot Urine (protein to creatinine ratio)	X	X	X	X	X	X	X	X	
Pregnancy Test ⁵	X	X	X	X	X	X	X	X	X
C3/C4, CRP ¹⁰			X				X	X	
B-Cells ¹⁰			X				X	X	
Anti-dsDNA and ANA ¹⁰			X				X	X	
Immunogenicity			X				X	X	
IgA, IgG and IgM ¹⁰	X	X	X	X	X	X	X	X	
Belimumab Administration and PK Sampling									
Cohort 1 Administration of Belimumab (Body weight \geq 50 kg) ^{6,9}	Once weekly (\pm 2 days) until Week 51 (inclusive)								

Procedure	Part B - Optional Treatment Extension - Days 86-365 (Weeks 13-52) [All participants]								
	Treatment Period							Follow-Up Period	
Study Day	Day 113 ±7 days	Day 141 ±7 days	Day 169 ±7 days	Day 211 ±7 days	Day 253 ±7 days	Day 309 ±7 days	Day 365 ±7 days	8-Week Follow-up ±7 days ¹	16-Week Follow-up ±7 days ^{1,2}
Study Week	Wk 16	Wk 20	Wk 24	Wk 30	Wk 36	Wk 44	Wk 52/EW ¹	Wk 60	Wk 68 ²
Cohort 2 Administration of Belimumab (Body weight \geq 30 kg to <50kg) ^{7,9}	Every 10 days(± 2 days) until Day 361 (inclusive)								
Cohort 3 Administration of Belimumab (Body weight <30kg) ^{8,9}	Every 2 weeks (±2 days) until Week 50 (inclusive)								
PK Sampling ¹⁰	X		X		X		X	X	

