1. If participants withdraw from treatment prior to Week 52, in addition to the 8- and 16-week follow-up visit and assessments, an early withdrawal (EW) visit should, if possible, be completed. The EW visit requires identical assessments and procedures to the Week 52 visit. The 8- and 16-week follow-up visits are **NOT** required for participants who are eligible for and are enrolled into the optional access extension phase.
2. 16-week follow-up requires a phone call to collect AEs, concomitant medications and report results of home urine pregnancy test (if applicable) for female participants. NOTE – the 16-week follow-up may be performed at a clinic visit per local requirement.
3. An abbreviated/symptom-driven exam can be done as described in Section 8.8.1
4. Please refer to Section 8.9.1 for the time period for collection of AEs/SAEs.
5. Urine pregnancy test is sufficient for all visits in Part B. A home pregnancy test (urine) will be provided to participants for the 16-week follow-up pregnancy assessment.
6. Cohort 1 (\geq 50 kg at baseline): Study drug to be administered weekly. Wherever the dosing days coincide with clinic visits IP administration in clinic is mandated. PK and/or biomarker sample collection, where specified, must be pre-dose at these visits.
7. Cohort 2 (\geq 30 kg - <50 kg at baseline): Study drug to be administered every 10 days. Wherever the dosing days coincide with clinic visits IP administration in clinic is mandated. PK and/or biomarker sample collection, where specified, must be pre-dose at these visits.
8. Cohort 3 (15 - <30 kg at baseline): Study drug to be administered every 2 weeks. Wherever the dosing days coincide with clinic visits IP administration in clinic is mandated. PK and/or sample collection, where specified, must be pre-dose at these visits.

9. In Part B the dosing frequency may be switched according to any change in body weight. Please refer to Section [6.6](#) Dose Modification. IF a participant switches dosing frequency due to weight changes during Part B, the last IP administration will be according to the schedule provided at Week44. Individual cases will be consulted with and resolved by the Medical Monitor.
10. Samples must be taken pre-dose where the dose is administered on a clinic visit day.

1.3.4. SOA 4 Optional Access Extension Phase - Applies exclusively to eligible participants who complete Part B

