5. For females of childbearing potential: urine pregnancy tests will be provided by sites. Participants will be required to perform a urine pregnancy test every 4 weeks throughout the treatment period (1 onsite and 2 at home). Home urine pregnancy tests will also be provided for the 8-week and 16-week follow-up period. The results of urine pregnancy tests conducted at home will be recorded in the subject diary cards and stored as part of the investigator's source documents. Only positive pregnancy test results will be reported to GSK during the optional access extension phase and will follow the guidance in Section 8.9.5.
6. Participants ≥50 kg at the start of the access extension phase: Study drug to be administered weekly. At home self-administration is encouraged.
7. Participants ≥30 kg - <50 kg at the start of the access extension phase: Study drug to be administered every 10 days. At home self-administration is encouraged.
8. Participants <30 kg at start of the access extension phase: Study drug to be administered every 2 weeks. At home self-administration is encouraged.
9. In the optional access extension phase the dosing frequency may be switched according to any change in body weight. Please refer to Section 6.6 Dose Modification.

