8.1. Screening Assessments

Information collected during the screening phase assessments represent key data that identify and define participant baseline status. This information is critical for evaluation of subsequent safety assessments.

Informed Consent

Informed consent will be obtained from the participant's parent/legally appointed representative prior to the initiation of any study procedures or study-specific data collection. The participant will provide their assent to participate in the study at the same time. Participants who turn 18 years old during the course of the study will provide their own informed consent.

Participants who give written consent will enter a screening period of up to 35 days. A participant may have treatment assigned when all screening procedures have been completed and eligibility criteria confirmed.

Screening Assessments

During the screening period the following assessments will be performed:

Demographic parameters will be captured: Date and year of birth, sex, race, and ethnicity.

Medical history/medication will be assessed as related to the exclusion criteria listed in Section [5.2](#). A complete medical history will be taken at the Screening Visit. Information

from the medical history is important to establish the baseline condition of the participant, and will impact the safety monitoring assessments during the study. Any significant medical conditions affecting the participant in the past 5 years should be recorded on the Medical conditions page of the eCRF. The history should include the following:

- Past or current conditions
- Prior surgical procedures
- Pharmacotherapy and chronic or current use of any medication or herbal preparation
- Prior use of belimumab
- Allergies and significant allergic reactions
- Significant infections, or history of recurrent infection, including urinary and respiratory tract infections
- Smoking history (current or previous smoker, number of cigarettes smoked per day)
- Cardiovascular medical history/risk factors (as detailed in the eCRF).

Pregnancy Test

A serum pregnancy test will be performed for females of child-bearing potential at the Screening Visit and a urine pregnancy test will be performed during each subsequent clinic visit. Refer to the pregnancy section (Section 8.9.5).

Full Physical Examination, Height, Weight, and Vital Signs

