8.8.4. Clinical Safety Laboratory Assessments

- A central laboratory will be used in this study.
- Refer to [Appendix 2](#) for the list of clinical laboratory tests to be performed and to the SoA (Section 1.3) for the timing and frequency.
- The investigator must review the laboratory report, document this review, and record any clinically relevant changes occurring during the study in the AE section of the CRF. The laboratory reports must be filed with the source documents. Clinically significant abnormal laboratory findings are those which are not associated with the underlying disease, unless judged by the investigator to be more severe than expected for the participant's condition.
- All laboratory tests with values considered clinically significantly abnormal during participation in the study or within 60 days after the last dose of study intervention should be repeated until the values return to normal or baseline or are no longer considered significantly abnormal by the investigator or medical monitor.
- If such values do not return to normal/baseline within a period of time judged reasonable by the investigator, the etiology should be identified and the sponsor notified.
- All protocol-required laboratory assessments, as defined in [Appendix 2](#), must be conducted in accordance with the laboratory manual and the SoA.
- Laboratory toxicity will be graded using the Adverse Event and Laboratory Value Severity Grading Table ([Appendix 2](#), Section 10.2.1). The Table is based upon publicly available Tables from the National Institute of Allergy and Infectious Disease Division of Microbiology and Infectious Diseases

(www.niaid.nih.gov) and Common Terminology Criteria for Adverse Events (CTCAE) Version 4.0 ([U.S. Department of Health and Human Services](#), 2010).

- Note: If a laboratory value is reported that requires withholding of further dosing, the site personnel must contact the parent/caregiver promptly to ensure no further injections are administered until reviewed with the investigator if the next administration would be away from the clinic.

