10.2. Appendix 2: Clinical Laboratory Tests

- The tests detailed in [Table 2](#) will be performed by the central laboratory.
- Protocol-specific requirements for inclusion or exclusion of participants are detailed in Section [5](#) of the protocol.
- Additional tests may be performed at any time during the study as determined necessary by the investigator or required by local regulations.
- Pregnancy testing
 - Refer to Section [5.1](#) Inclusion Criteria for screening pregnancy criteria.
 - Pregnancy testing (urine or serum as required by local regulations) should be conducted at monthly intervals during intervention
 - Pregnancy testing (urine or serum as required by local regulations) should be conducted at the end of relevant systemic exposure.
 - Additional serum or urine pregnancy tests may be performed, as determined necessary by the investigator or required by local regulation, to establish the absence of pregnancy at any time during the participant's participation in the study.

Table 2 **Protocol-Required Safety Laboratory Assessments**

Laboratory Assessments	Parameters			
Hematology	Platelet Count	RBC Indices: MCV MCH %Reticulocytes	WBC count with Differential: Neutrophils Lymphocytes Monocytes Eosinophils Basophils	
	RBC Count			
	Hemoglobin			
	Hematocrit			
Clinical Chemistry ¹	Calcium	Potassium	Aspartate Aminotransferase (AST)/ Serum Glutamic-Oxaloacetic Transaminase (SGOT)	Total bilirubin
	Calcium corrected for Albumin Inorganic Phosphate	Sodium	Alanine Aminotransferase (ALT)/ Serum Glutamic-Pyruvic Transaminase (SGPT)	Total Protein

Laboratory Assessments	Parameters			
	Carbon dioxide	Magnesium	Alkaline phosphatase	Albumin
	Glucose (nonfasting)		Gamma glutamyl transpeptidase (GGT)	Creatinine
	Uric acid	Blood urea nitrogen (BUN)	BUN/creatinine ratio	Estimated Creatinine Clearance/GFR (Schwartz ²)
Routine Urinalysis	
 pH, glucose, protein, blood, ketones, occult blood by dipstick Microscopic examination (if blood or protein is abnormal) 			
Biological markers	
 BLyS protein Serum complement (C3 and C4) C-Reactive Protein (CRP) Peripheral lymphocytes including B lymphocytes (CD20+, CD20+/27+ memory, CD20+/27– naïve, CD19+/27br/38br 'SLE subset'). 			
Immunoglobulins	
 Serum immunoglobulin isotypes: IgG, IgM, IgA 			
PK	
 Blood collection 			

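### From Week 24 to Week 52, SOA 3 schedules pregnancy tests 6 to 8 weeks apart, although Appendix 2 calls for monthly testing during treatment

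*Protocol*

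**What the plan says.** Protocol Appendix 2 (Section 10.2) sets the interval: "Pregnancy testing (urine or serum as required by local regulations) should be conducted at monthly intervals during intervention". It also leaves room for more: "Additional serum or urine pregnancy tests may be performed, as determined necessary by the investigator or required by local regulation".

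Section 8.8.4 refers the reader to Appendix 2 "for the list of clinical laboratory tests to be performed and to the SoA (Section 1.3) for the timing and frequency", and adds that the assessments in Appendix 2 are to be carried out as the laboratory manual and the SoA lay down. Section 8 makes adherence to the SoA a requirement. Section 8.1 says that, after the serum test at screening, "a urine pregnancy test will be performed during each subsequent clinic visit".

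SOA 3 (Section 1.3.3) marks a pregnancy test at Weeks 16, 20, 24, 30, 36, 44 and 52 and at the two follow-up contacts. Its footnote 5 reads "Urine pregnancy test is sufficient for all visits in Part B" and then "A home pregnancy test (urine) will be provided to participants for the 16-week follow-up pregnancy assessment"; it mentions no other home kit. Dosing in Part B runs to Week 51 (weekly), Day 361 (every 10 days) or Week 50 (every 2 weeks).

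SOA 4, for the optional access extension, has visits 12 weeks apart but says: "Participants will be required to perform a urine pregnancy test every 4 weeks throughout the treatment period (1 onsite and 2 at home".

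**The concern.** A site that follows SOA 3 exactly will not meet the Appendix 2 interval once the visits spread out after Week 24. It would have to arrange tests that nothing schedules and for which SOA 3 supplies no kit. The protocol gives no reason for longer intervals in the second half of Part B. It solves the same problem in the extension phase, where visits are further apart still.

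Under Section 7.1, pregnancy means withdrawal from study agent, and under Section 8.9.5 it must be reported within 24 hours of the site learning of it. Both depend on detection. Between Part B visits the drug is generally injected at home, so with no test and no visit there is no planned point at which an undetected pregnancy would stop dosing.

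**Working it through.** **Inputs.**
- Part B visit days (SOA 3): 113, 141, 169, 211, 253, 309 and 365, each ±7 days. Checking (day − 1)/7 gives Weeks 16, 20, 24, 30, 36, 44 and 52, as labelled.
- Last Part A test: Day 85 for Cohorts 1 and 3 (SOA 1), Day 81 for Cohort 2 (SOA 2).
- Dosing intervals: 7, 10 and 14 days (Section 4.1).
- Planned enrolment: 28 (Section 9.2).
- Contraceptive failure rate: below 1% (Section 5.1), given per year in Appendix 4. A rate of 5% per year is my assumption, used only to show a range.

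**Step 1. Where the plan meets its own interval.** The longest Part A gap is 28 days (Cohorts 1 and 3) or 30 days (Cohort 2). From the end of Part A to Week 24 the gaps are 28, 28 and 28 days; for Cohort 2 the first is 113 − 81 = 32 days. Testing is about monthly up to Week 24.

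**Step 2. Week 24 onward.** The range in the last column is the nominal gap ±14 days, because both visits can move by 7 days.

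| Interval | Days | Nominal gap | Range with windows |
|---|---|---|---|
| Week 24 to 30 | 211 − 169 | 42 days (6 weeks) | 28 to 56 days |
| Week 30 to 36 | 253 − 211 | 42 days (6 weeks) | 28 to 56 days |
| Week 36 to 44 | 309 − 253 | 56 days (8 weeks) | 42 to 70 days |
| Week 44 to 52 | 365 − 309 | 56 days (8 weeks) | 42 to 70 days |

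If Week 24 falls as late as possible and Week 52 as early as possible, the mean gap is still (358 − 176)/4 = 45.5 days. The windows cannot restore a monthly interval.

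**Step 3. Shortfall.**
- Tests after Week 24: 4 scheduled. A four-week interval needs (365 − 169)/28 = 7. The mean scheduled gap is 28/4 = 7 weeks.
- Time more than 4 weeks after the last test: (6 − 4) + (6 − 4) + (8 − 4) + (8 − 4) = 12 weeks; 12/40 = 30% of Part B. In Cohort 2 the 32-day first gap adds 4 days.
- With a calendar month of 4.35 weeks: 2(6 − 4.35) + 2(8 − 4.35) = 10.6 weeks; 10.6/40 = 26.5%.

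**Step 4. Exposure between tests.** Doses in 56 days: 56/7 = 8, 56/10 = 5.6, 56/14 = 4. Doses in 28 days: 4, 2.8, 2. The 8-week figures are the worst case, with conception just after a test.

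For the average case, assume conception is equally likely at any time in Weeks 24 to 52 and count the wait to the next test as Σg²/(2Σg), where g is the gap in weeks:
- SOA 3: (36 + 36 + 64 + 64)/(2 × 28) = 3.6 weeks.
- Four-weekly: (7 × 16)/(2 × 28) = 2.0 weeks.
- Difference: about 1.6 weeks, or roughly 1.6 weekly, 1.1 ten-day or 0.8 two-weekly doses.

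**Step 5. How often this could arise.** Assume all 28 participants are of childbearing potential and stay to Week 52. Expected pregnancies in Weeks 24 to 52 are then 28 × 0.01 × 28/52 = 0.15, or 28 × 0.05 × 28/52 = 0.75 at the assumed 5%. Boys and premenarchal girls reduce both figures.

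**The case against.** The best reply is that nothing forbids monthly testing. Appendix 2 stands as its own instruction, uses the word should, and allows extra tests. No clause states in terms that the SoA outranks it. Section 8.8.4 is about laboratory tests, and Table 2 lists the hCG test under screening, so applying that section to Part B urine tests is an inference. Much operational detail is left to the Study Reference Manual, which is not among the documents and might supply interim kits.

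The consequence is also modest. The average extra delay is about 1.6 weeks, not 4, and few pregnancies are expected. At 0.15 pregnancies and weekly dosing, that is about 0.15 × 1.6 = 0.24 extra doses over the whole trial. The risk table in Section 2.3.1 names no embryofetal risk.

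The points about size stand, and so does the limit set by the unseen manual. The point about permission does not settle the matter. Section 8.8.4 sends sites to the SoA for timing and frequency and wants Appendix 2 assessments done in accordance with it, Section 8 requires adherence to the SoA, and Section 8.1 links urine tests to clinic visits. The one home kit in SOA 3 is for follow-up. A site could add tests on its own initiative, but a stated interval should not depend on that, particularly when SOA 4 shows how to schedule it.

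**Conclusion.** The concern holds. From Week 24 to Week 52, SOA 3 by itself delivers pregnancy tests every 6 to 8 weeks against the monthly interval in Appendix 2: 4 tests instead of about 7, with 30% of Part B more than four weeks after the last test (26.5% on a calendar month). Up to Week 24 the two texts agree, apart from the 32-day first gap in Cohort 2.

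This is a gap in safety monitoring, and its size is the time taken to find a pregnancy rather than the number that occur. It has no bearing on the sample size, the endpoints or the SAP. The conclusion rests on reading the SoA as the schedule that sites will follow, and on the Study Reference Manual not already providing interim tests. The gap arithmetic uses only the visit days printed in SOA 3. The pregnancy counts are upper bounds for the failure rates stated, and the 5% rate is assumed. The correction is cheap and delivers the protocol's own interval, so it should be made.

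**What to change.** Add to SOA 3 footnote 5: females of childbearing potential perform a home urine pregnancy test at Weeks 28, 32, 40 and 48, record the result in a diary as in SOA 4, and have any positive result reported under Section 8.9.5 before the next dose. The tests then fall at Weeks 24, 28, 30, 32, 36, 40, 44, 48 and 52, with nominal gaps of 4, 2, 2, 4, 4, 4, 4 and 4 weeks. Weeks 27, 33, 40 and 48 would do as well, with gaps of 3, 3, 3, 3, 4, 4, 4 and 4 weeks.

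The cost is four kits and four diary entries per relevant participant, at most 4 × 28 = 112 kits, with no added visit or blood draw. The Part B injection diary would need a field for the result. As a protocol amendment the change needs ethics committee approval (Section 10.1.1). The SAP (Section 8.1.2) already describes on-treatment data collection in the past tense, so in this trial it can help only participants still in Part B. Rewording Appendix 2 to match SOA 3 would remove the mismatch on paper and change nothing for participants.

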10.2.1. Adverse Event and Laboratory Value Severity Grade Table

HEMATOLOGY	GRADE 1 MILD	GRADE 2 MODERATE	GRADE 3 SEVERE	GRADE 4 POTENTIALLY LIFE-THREATENING
Hemoglobin	> 9.5 - 11.0 g/dL	> 8.0 – 9.5 g/dL	6.5 - 8.0 g/dL	< 6.5 g/dL
Leukocytes	3000-3999/mm ³	2000-2999/mm ³	1000-1999/mm ³	< 1000/mm ³
Absolute Neutrophil Count	1500-1999/mm ³	1000-1499/mm ³	500-999/mm ³	< 500/mm ³
Platelets	75,000 - 99,999/mm ³	50,000 – 74,999/mm ³	25,000 - 49,999/mm ³	< 25,000/mm ³
Prothrombin Time (PT)	> 1.0-1.25 x ULN*	> 1.25-1.5 x ULN	> 1.5-3.0 x ULN	> 3.0 x ULN
Partial Thromboplastin Time (PTT)	> 1.0-1.66 x ULN	> 1.66-2.33 x ULN	> 2.33-3.0 x ULN	> 3.0 x ULN
Methemoglobin	5.0-10.0 %	10.1-15.0 %	15.1-20.0 %	> 20%
Lymphocyte count**	<LLN - 800/mm ³ ; <LLN - 0.8 x 10e9 /L	<800 - 500/mm ³ ; <0.8 - 0.5 x 10e9 /L	<500 - 200/mm ³ ; <0.5 - 0.2 x 10e9 /L	<200/mm ³ ; <0.2 x 10e9 /L

(continued)

*ULN = Upper Limit of Normal

**Lymphopenia calculated from CTCAE table

Adverse Event and Laboratory Value Severity Grade Table (continued)

CARDIOVASCULAR		GRADE 1 MILD	GRADE 2 MODERATE	GRADE 3 SEVERE	GRADE 4 POTENTIALLY LIFE- THREATENING
Cardiac Arrhythmia	-		Asymptomatic/transient; dysrhythmia; no treatment req	Recurrent/persistent dysrhythmia. Symptomatic; treatment req	Unstable dysrhythmia hospitalization and treatment required
Hypotension	Transient orthostatic hypotension, no treatment		Symptoms correctable with oral fluid treatment	IV fluid req, no hospitalization req	Hospitalization req
Hypertension	Transient, increase > 20 mm/Hg; no treatment		Recurrent; chronic increase > 20 mm/Hg, treatment req	Acute treatment req; out subject hospitalization possible	Hospitalization req
Pericarditis	Minimal effusion		Mild/moderate asymptomatic effusion, no treatment	Symptomatic effusion, pain, ECG changes	Tamponade OR pericardiocentesis OR surgery req
Hemorrhage, Blood Loss	-		Mildly symptomatic; no treatment required	Gross blood loss OR 1-2 units transfused	Massive blood loss OR > 2 units transfused

(continued)

Adverse Event and Laboratory Value Severity Grade Table (continued)

	GRADE 1 MILD	GRADE 2 MODERATE	GRADE 3 SEVERE	GRADE 4 POTENTIALLY LIFE-THREATENING
CHEMISTRIES				
Sodium				
Hyponatremia	130-135 meq/L	123-129 meq/L	116-122 meq/L	< 116 meq/L
Hypernatremia	146-150 meq/L	151-157 meq/L	158-165 meq/L	> 165 meq/L
Potassium				
Hypokalemia	3.0-3.4 meq/L	2.5-2.9 meq/L	2.0-2.4 meq/L	< 2.0 meq/L
Hyperkalemia	5.6-6.0 meq/L	6.1-6.5 meq/L	6.6-7.0 meq/L	> 7.0 meq/L
Phosphate				
Hypophosphatemia	2.0-2.4 mg/dL	1.5-1.9 mg/dL	1.0-1.4 mg/dL	< 1.0 mg/dL
Calcium- (Corrected For Albumin)				
Hypocalcemia	7.8-8.4 mg/dL	7.0-7.7 mg/dL	6.1-6.9 mg/dL	< 6.1 mg/dL
Hypercalcemia	10.6-11.5 mg/dL	11.6-12.5 mg/dL	12.6-13.5 mg/dL	>13.5 mg/dL
Magnesium				
Hypomagnesemia	1.2-1.4 meq/L	0.9-1.1 meq/L	0.6-0.8 meq/L	< 0.6 meq/L
Albumin				
Hypoalbuminemia	3.00-3.49 g/dL	2.50-2.99 g/dL	2.00-2.49 g/dL	< 2.00 g/dL
Bilirubin (Total)				
Hyperbilirubinemia (Total)	> 1.0-1.5 x ULN	> 1.5-2.5 x ULN	> 2.5-5 x ULN	> 5 x ULN
Glucose				
Hypoglycemia	55-64 mg/dL	40-54 mg/dL	30-39 mg/dL	< 30 mg/dL
Hyperglycemia (nonfasting & no prior diabetes)	116-160 mg/dL	161-250 mg/dL	251-500 mg/dL	> 500 mg/dL
Triglycerides	151-399 mg/dL	400-750 mg/dL	751-1200 mg/dL	> 1200 mg/dL
Creatinine	> 1.0-1.5 x ULN	> 1.5-3.0 x ULN	> 3.0-6.0 x ULN	> 6.0 x ULN

Adverse Event and Laboratory Value Severity Grade Table (continued)

	GRADE 1 MILD	GRADE 2 MODERATE	GRADE 3 SEVERE	GRADE 4 POTENTIALLY LIFE-THREATENING
CHEMISTRIES (continued)				
Uric Acid				
Hyperuricemia	7.5-10.0 mg/dL	10.1-12.0 mg/dL	12.1-15.0 mg/dL	> 15.0 mg/dL
Liver Transferases (AST, ALT, and GGT)	1.25-2.5 x ULN	> 2.5-5.0 x ULN	> 5.0-10.0 x ULN	> 10.0 x ULN
Alkaline Phosphatase	1.25-2.5 x ULN	> 2.5-5.0 x ULN	> 5.0-10.0 x ULN	> 10.0 x ULN
Pancreatic Enzymes				
Amylase	> 1.0-1.5 x ULN	> 1.5-2.0 x ULN	> 2.0-5.0 x ULN	> 5.0 x ULN
Pancreatic amylase	> 1.0-1.5 x ULN	> 1.5-2.0 x ULN	> 2.0-5.0 x ULN	> 5.0 x ULN
Lipase	> 1.0-1.5 x ULN	> 1.5-2.0 x ULN	> 2.0-5.0 x ULN	> 5.0 x ULN
Hypoglobulinemia (IgG)*	550-700 mg/dL	400-549 mg/dL	250-399 mg/dL	< 250 mg/dL

(continued)

*[Eibl, 1995; Goldfarb, 2001; Yamani, 2001].

Adverse Event and Laboratory Value Severity Grade Table (continued)

GASTROINTESTINAL	GRADE 1 MILD	GRADE 2 MODERATE	GRADE 3 SEVERE	GRADE 4 POTENTIALLY LIFE- THREATENING
Nausea	Mild OR transient; reasonable intake maintained	Mod discomfort OR intake decreased for < 3 days	Severe discomfort OR minimal intake for ≥ 3 days	Hospitalization required
Vomiting	Mild OR transient; 2-3 episodes/day OR mild vomiting lasting < 1 week	Mod OR persistent; 4-5 episodes per day; OR vomiting lasting ≥ 1 week	Severe vomiting of all foods/fluids in 24 hours OR orthostatic hypotension OR IV treatment req	Hypotensive shock OR hospitalization required for IV treatment req
Diarrhea	Mild or transient; 3-4 loose stools per day OR mild diarrhea lasting < 1 week	Mod OR persistent; 5-7 loose stools per day or diarrhea lasting ≥ 1 week	Bloody diarrhea; OR orthostatic hypotension OR > 7 loose stools/day OR IV treatment req	Hypotensive shock OR hospitalization req
Oral Discomfort/Dysphagia	Mild discomfort, no difficulty swallowing	Difficulty swallowing but able to eat and drink	Unable to swallow solids	Unable to drink fluids; IV fluids req
Constipation	Mild	Moderate	Severe	Distention with vomiting

Adverse Event and Laboratory Value Severity Grade Table (continued)

	GRADE 1 MILD	GRADE 2 MODERATE	GRADE 3 SEVERE	GRADE 4 POTENTIALLY LIFE-THREATENING
RESPIRATORY				
Cough (for aerosol studies)	Transient; no treatment	Treatment associated cough; inhaled bronchodilator	Uncontrolled cough; systemic treatment req	
Bronchospasm Acute	Transient; no treatment; FEV1 70% to < 80% (or peak flow)	treatment req; normalizes with bronchodilator; FEV1 50% to < 70% (or peak flow)	No Normalization with bronchodilator; FEV 25% to < 50% (or peak flow), retractions	Cyanosis; FEV1 < 25% (or peak flow) OR intubated
Dyspnea	Dyspnea on exertion	Dyspnea with normal activity	Dyspnea at rest	Dyspnea requiring O2 therapy

	GRADE 1 MILD	GRADE 2 MODERATE	GRADE 3 SEVERE	GRADE 4 POTENTIALLY LIFE-THREATENING
URINALYSIS				
Proteinuria				
Dispstick				
Protein	1 +	2-3 +	4 +	Nephrotic syndrome
Spot Urine:	0.2-1.0	> 1.0-2.0	> 2.0-3.5	> 3.5
Protein:Creatinine Ratio mg/mg				
24 Hour Urine:	200 mg - 1g loss/day	> 1-2 g loss/day	> 2-3.5 g loss/day	Nephrotic syndrome OR > 3.5 g loss/day
Protein				
Hematuria	Microscopic only > 3 to < 10 RBC/hpf	Gross, No clots ≥ 10 RBC/hpf	Gross plus clots OR RBC casts	Obstructive OR transfusion required

RBC = red blood cell; hpf = high power field.

Adverse Event and Laboratory Value Severity Grade Table (continued)

MISCELLANEOUS	GRADE 1 MILD	GRADE 2 MODERATE	GRADE 3 SEVERE	GRADE 4 POTENTIALLY LIFE- THREATENING
Fever (oral > 12 hours)	37.7-38.5°C or 100.0-101.5°F	38.6-39.5°C OR 101.6-102.9°F	39.6-40.5°C OR 103-105°F	> 40.5°C OR > 105°F
Headache	Mild; No treatment req	Mod; or non-narcotic analgesia treatment	Severe; OR responds to initial narcotic treatment	Intractable; OR requiring repeated narcotic treatment
Allergic Reaction	Pruritus without rash	Localized urticaria	Generalized urticaria angioedema	Anaphylaxis
Cutaneous/Rash/Dermatitis	Erythema, pruritus rash OR dry desquamation	Diffuse maculopapular OR dry desquamation	Vesiculation OR moist desquamation ulceration	ANY ONE: mucous membrane involvement, suspected Stevens-Johnson (TEN), erythema multiforme, necrosis req surgery, exfoliative dermatitis
Local Reaction (secondary to parenteral treatment- not vaccination or skin test)	Erythema	Induration < 10 mm OR inflammation OR phlebitis	Induration > 10 mm OR ulceration	Necrosis of skin
Fatigue	Normal activity Reduced < 25%	Normal activity Reduced 25-50%	Normal activity reduced > 50%; cannot work	Unable to care for self

Adverse Event and Laboratory Value Severity Grade Table (continued)

NEUROLOGIC	GRADE 1 MILD	GRADE 2 MODERATE	GRADE 3 SEVERE	GRADE 4 POTENTIALLY LIFE- THREATENING
Neuro-cerebellar	Slight incoordination OR dysdiadochokinesia	Intention tremor OR dysmetria OR slurred speech OR nystagmus	Ataxia requiring assistance to walk or arm incoordination interfering with ADLs	Unable to stand
Neuro-psych/mood		none	Severe mood changes requires medical intervention	Acute psychosis requiring Hospitalization
Paresthesia (burning, tingling, etc)	Mild discomfort; no treatment needed	Mod discomfort non-narcotic analgesia req	Severe discomfort; OR narcotic analgesia req with symptomatic improvement	Incapacitating; OR not responsive to narcotic analgesia
Neuro-motor	Mild weakness in muscle of feet but able to walk and/or mild increase or decrease in reflexes	Mod weakness in feet (unable to walk on heels and/or toes), mild weakness in hands, still able to do most hand tasks and/or loss of previously present reflex or development of hyperreflexia and/or unable to do deep knee bends due to weakness	Marked distal weakness (unable to dorsiflex toes or foot drop), and mod proximal weakness ie, in hands interfering with ADLs and/or requiring assistance to walk and/or unable to rise from chair unassisted	Confined to bed or wheelchair because of muscle weakness
Neuro-sensory	Mild impairment sensations, (ie, vibratory, pinprick, hot/cold in great toes) in focal area or symmetrical distribution	Mod impairment mod de-sensation, (ie, of vibratory, pinprick, hot/cold to ankles) and/or joint position or mild impairment that is not symmetrical.	Severe impairment (dec or loss of sensation to knees or wrists) or loss of sensation of at least mod degree in multiple different body areas (ie, upper and lower extremities)	Sensory loss involves limbs and trunk

10.3. Appendix 3: Adverse Events: Definitions and Procedures for Recording, Evaluating, Follow-up, and Reporting

